5. SAFETY

The summary tables and listings will be provided separately for each indication and overall population, separately.

5.1. Clinical Laboratory Tests

Change from baseline summaries will be presented for chemistry and hematology laboratory tests at scheduled time points.

Number and percentage of subjects with markedly abnormal laboratory values for hematology and chemistry will be presented over time. Listings of markedly abnormal laboratory findings will be provided.

Shift tables will be provided summarizing the shift in laboratory values from baseline to week 14 and week 24 with respect to abnormality criteria (low, normal, high).

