### 4.1. Inclusion Criteria

All potential subject must satisfy all of the following criteria to be enrolled in the study:

1. Are man or woman 18 years of age or older.
2. Women of childbearing potential or men capable of fathering children must be using adequate birth control measures (eg, abstinence, oral contraceptives, intrauterine device, barrier method with spermicide, surgical sterilization) during the study and must be willing to use such birth control measures for 6 months after receiving the last administration of study drug. Female subjects of childbearing potential must test negative for pregnancy.
3. Are considered eligible per the following tuberculosis (TB) screening criteria:
  - a. Have no history of TB prior to screening.
  - b. Have no signs or symptoms suggestive of active TB upon medical history and/or physical examination.
  - c. Have had no recent close contact with a person with active TB, or if there has been such contact, will be referred to a physician specializing in TB to undergo additional evaluation and, if warranted, receive appropriate treatment for latent TB prior to or simultaneously with the first administration of study drug.
  - d. Within 6 weeks prior to the first administration of study drug, have a negative QuantiFERON-TB Gold and a negative tuberculin skin test result, or have a newly identified positive QuantiFERON-TB Gold or tuberculin skin test result during screening in which active TB has been ruled out and for which appropriate treatment for latent TB has been initiated either prior to or simultaneously with the first administration of study drug.
  - e. Have a chest radiograph (both posterior-anterior and lateral views), taken within 3 months prior to the first administration of study drug and read by a qualified radiologist, with no evidence of current active TB or old inactive TB.
4. Have screening laboratory test results as follows:
  - a. Haemoglobin more than or equal to 8.5 g/dL
  - b. White blood cells (WBC) count more than or equal to  $3.5 \times 10^3$  cells/micro-litre
  - c. Platelets more than or equal to  $100 \times 10^3$  cells/micro-litre

- d. Serum alanine aminotransferase (ALT) and aspartate aminotransferase (AST) level not exceeding 1.5 times the upper limits of normal for the laboratory conducting the test.
- e. Serum creatinine not exceeding 1.5 mg/dL

5. Are willing and able to adhere to the study visit schedule and other protocol requirements.

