**12.1.3. Severity Criteria**

The severity assessment for an adverse event or serious adverse event should be completed using the National Cancer Institute Common Terminology Criteria for Adverse Events (NCI-CTCAE) Version 4.03. Any adverse event or serious adverse event not listed in the NCI-CTCAE Version 4.03 will be graded according to investigator clinical judgment by

- Grade 1: (Mild): Awareness of symptoms that are easily tolerated, causing minimal discomfort and not interfering with everyday activities.
- Grade 2: (Moderate): Sufficient discomfort is present to cause interference with normal activity.
- Grade 3: (Severe): Extreme distress, causing significant impairment of functioning or incapacitation. Prevents normal everyday activities.
- Grade 4: Life-threatening or disabling adverse event
- Grade 5: Death related to the adverse event

The investigator should use clinical judgment in assessing the severity of events not directly experienced by the subject (e.g., laboratory abnormalities).

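### The low/normal/high laboratory shift table in SAP 5.1 cannot show further worsening in patients who enter already out of range, other planned outputs cover this only in part, and its Week 14 panel has no scheduled routine laboratory data

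*SAP*

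**What the plan says.** SAP 5.1 (Clinical Laboratory Tests) plans three kinds of output for chemistry and haematology:

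- Change-from-baseline summaries at scheduled time points. SAP 2.5 requires continuous summaries to include the minimum and maximum.
- A count: "Number and percentage of subjects with markedly abnormal laboratory values for hematology and chemistry will be presented over time". It is accompanied by patient-level output: "Listings of markedly abnormal laboratory findings will be provided". Neither the SAP nor the protocol says what value counts as markedly abnormal.
- Shift tables "summarizing the shift in laboratory values from baseline to week 14 and week 24", classified "with respect to abnormality criteria (low, normal, high".

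Protocol 4.1, inclusion criterion 4, sets the screening limits. ALT and AST must be at a "level not exceeding 1.5 times the upper limits of normal for the laboratory conducting the test". The haemoglobin limit is "Haemoglobin more than or equal to 8.5 g/dL". White cells, platelets and creatinine also have fixed cut-offs rather than the local normal range.

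Laboratory changes can also reach the adverse event data. Protocol 9.2 has the investigator record clinically relevant changes as adverse events. The definition in Protocol 12.1.1 includes aggravation of a baseline condition and abnormal laboratory results. Protocol 12.1.3 says the severity assessment "should be completed using the National Cancer Institute Common Terminology Criteria for Adverse Events", version 4.03, and SAP 5.2 tabulates treatment-emergent events by severity.

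The Time and Events Schedule, and the visit lists in Protocol 9.1.2 and 9.1.3, place the routine laboratory panel at screening and Week 24 only.

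**The concern.** A shift table is meant to show, patient by patient, who moved from an acceptable value to a worse one. With a single category on each side of normal, a patient who starts in the high or low category has nowhere further to go in that direction. For ALT and AST the eligibility rule expressly allows such a start. For haemoglobin it does so in practice, given a limit of 8.5 g/dL.

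Safety is the primary objective, and the safety endpoint includes laboratory events. The shift table is the only categorical laboratory output whose categories are stated and do not depend on investigator judgement. If it cannot separate a trivial change from a severe one in these patients, a reader must rely on outputs that are undefined or discretionary.

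**Working it through.** The plan states no figure to reproduce: the sample size of 100 is a regulatory requirement and no hypothesis is tested. The check applies the three-category rule to baselines that eligibility allows, then asks what the other outputs would show.

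**Inputs.** ALT/AST ceiling 1.5 x ULN and haemoglobin floor 8.5 g/dL (Protocol 4.1); categories low, normal, high (SAP 5.1); about 50 patients per indication and 100 overall (SAP 1.4). Local reference limits are not in the documents, so a lower haemoglobin limit of 11 to 13 g/dL is assumed. The patients below are hypothetical.

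**Step 1: the shift rule.** A value is low if below the lower limit, high if above the upper limit, and otherwise normal.

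| Baseline to follow-up | Change | Cell |
|---|---|---|
| ALT 1.2 to 1.4 x ULN | +0.2 | high to high |
| ALT 1.4 to 10 x ULN | +8.6 | high to high |
| ALT 1.5 to 20 x ULN | +18.5 | high to high |
| ALT 1.0 to 10 x ULN | +9.0 | normal to high |
| Haemoglobin 8.5 to 6.0 g/dL | -2.5 | low to low |

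The second row is a 10 / 1.4 = 7.1-fold rise and shares a cell with the first. The fourth row, from a normal baseline, is shown. The haemoglobin result is the same for assumed lower limits of 11, 12 and 13 g/dL.

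**Step 2: the other outputs, for ALT 1.4 to 10 x ULN.**

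- Change from baseline: with n = 50 this patient moves the mean by 8.6 / 50 = 0.17 x ULN. The maximum change would print as 8.6 x ULN if ALT is summarised in ULN multiples, which the SAP does not specify. One maximum does not say how many patients worsened or from what baseline status.
- Markedly abnormal count and listing: the patient appears if the value meets a criterion that is not stated.
- Adverse events: the patient appears, graded, if the investigator judges the change clinically relevant.

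**Step 3: timing.** SAP 5.1 promises shifts at Week 14 and Week 24. The Week 14 visit includes ESR and CRP but not the routine haematology and chemistry panel. The Week 14 routine panel therefore has no scheduled data, and each patient has one scheduled post-baseline routine value. The window tables in SAP 2.1 cover vital signs, urine pregnancy tests, ASAS20 and ACR20, so the handling of unscheduled laboratory values is unspecified.

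**Step 4: illustrative size (both inputs assumed).** Let m be the number entering out of range on an analyte and r the risk of severe worsening in them. The chance of at least one case in a no-shift cell is 1 - (1 - r)^m.

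- 5% of 100 gives m = 5; with r = 0.01: 1 - 0.99^5 = 0.049.
- 30% of 100 gives m = 30; with r = 0.05: 1 - 0.95^30 = 0.785.

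The range is about 5% to 79%, too wide to be more than an illustration.

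**The case against.** The strongest reply is that the shift table is one of several descriptive outputs. An extreme change would print as a maximum. A sensible absolute threshold for markedly abnormal would catch an extreme value whatever the baseline. A worsened laboratory abnormality is reportable as an adverse event and graded. The safety endpoint is measured through adverse event reporting, not this table, and no test depends on it. Protocol section 11 also promises subject-wise listings in general terms.

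Most of this stands. A reader might infer that severe worsening in these patients disappears from the safety analysis; the documents do not support that. Nor do they support saying that a value from an unscheduled test never enters the table. SAP 5.1 does not exclude such values; SAP 2.1 simply gives no laboratory rule. And no count of affected patients can be claimed, because the documents give neither the share with out-of-range baselines nor the local ranges. For white cells, platelets and creatinine it cannot be shown from the documents that the cut-offs admit out-of-range values.

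What does not stand is that the other outputs close the gap. The threshold that would do so is missing from both documents. The adverse event route rests on clinical relevance as judged by the investigator in an open-label study, and Protocol 11.4 likewise leaves clinical significance of laboratory results to the principal investigator.

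**Conclusion.** The point holds as a limitation of one table that the rest of the plan covers only in part. For any patient above the ULN on ALT or AST at entry, or below the local lower limit for haemoglobin, the planned shift cannot show further worsening in that direction, however large. This follows from the category definition and the eligibility limits; only the haemoglobin part needs an assumption, namely a local lower limit above 8.5 g/dL. The undefined markedly abnormal criterion is the more consequential gap, since that output should catch these patients. The Week 14 shift is a plain mismatch with the visit schedule.

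The number of patients affected is unknown. No sample size, error rate or efficacy result changes. This is a worthwhile, inexpensive improvement to the safety reporting, not a flaw that invalidates it.

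**What to change.** In SAP 5.1:

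1. Keep the low/normal/high shift and add a shift in NCI-CTCAE v4.03 grade, the standard the protocol already uses for severity and supplies to sites. Show baseline to Week 24 or end of treatment, and baseline to worst post-baseline value, including unscheduled tests where these are in the database. Cover ALT, AST, bilirubin, creatinine, haemoglobin, white cells/neutrophils and platelets, using local reference ranges.
2. Define markedly abnormal by the same grades, for example Grade 3 or above, with a rule that the grade must have worsened from baseline.
3. Reconcile the Week 14 shift with the Time and Events Schedule, and state how laboratory values are assigned to visits.

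The cost is SAP text and extra programming. The sponsor must first confirm that local reference ranges and unscheduled results are in the database: Protocol 17.2.2 asks sites for a copy of their normal ranges, if applicable, which does not establish that they are held as data.

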5.2. Adverse Events

All Adverse Events will be coded by system organ class and preferred term using the latest Medical Dictionary for Regulatory Activities version (MedDRA 24.0).

Any AE occurring at or after the initial administration of study drug through the day of last dose plus 8 weeks is considered to be treatment emergent. If the event occurs on the day of the initial administration of study drug, and either event time or time of administration are missing, then the event will be assumed to be treatment emergent. If the event date is recorded as partial or completely missing, then the event will be considered to be treatment emergent unless it is known to be prior to the first administration of study drug based on partial onset date or resolution date.

All reported treatment-emergent adverse events will be included in the analysis. For each adverse event, the number and percentage of subjects who experience at least 1 occurrence of the given event will be summarized.

Summary tables will be provided for:

- AEs
- Serious AEs (SAEs)
- TEAEs leading to discontinuation of study agent
- TEAEs by severity
- TEAEs by relationship to study drug
- TEAEs of special Interest by SOC and PT
- TEAEs by SOC and PT

In addition to the summary tables, listings will be provided for subjects who had:

- Any AE
- SAEs
- AEs leading to discontinuation of study drug
- Deaths due to AE.

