#### **4.2. Exclusion Criteria**

1. Are pregnant, nursing, or planning a pregnancy or fathering a child during the study or within 6 months after receiving the last administration of study drug.

2. Have a known hypersensitivity to human immunoglobulin proteins or other components of golimumab.
3. Have been treated with any investigational drug within 5 half-lives of that drug prior to the first administration of study drug.
4. Have a history of latent or active granulomatous infection, including histoplasmosis, or coccidioidomycosis, prior to screening. Refer to inclusion criteria for information regarding eligibility with a history of latent TB.
5. Have a chest radiograph within 3 months prior to the first administration of study drug that shows an abnormality suggestive of a malignancy or current active infection, including TB.
6. Have had a nontuberculous mycobacterial infection or opportunistic infection (eg, cytomegalovirus, pneumocystosis, aspergillosis) within 6 months prior to screening.
7. Have received, or are expected to receive, any live virus or bacterial vaccination within 3 months before the first administration of study drug, during the study, or within 6 months after the last administration of study drug.
8. Have a history of an infected joint prosthesis, or have received antibiotics for a suspected infection of a joint prosthesis, if that prosthesis has not been removed or replaced.
9. Have had a serious infection (including but not limited to, hepatitis, pneumonia, sepsis, or pyelonephritis), or have been hospitalized for an infection, or have been treated with IV antibiotics for an infection within 2 months prior to first administration of study drug. Less serious infections (eg, acute upper respiratory tract infection, simple urinary tract infection) need not be considered exclusionary at the discretion of the investigator.
10. Have a history of, or ongoing, chronic or recurrent infectious disease, including but not limited to, chronic renal infection, chronic chest infection (eg, bronchiectasis), sinusitis, recurrent urinary tract infection (eg, recurrent pyelonephritis, chronic non-remitting cystitis), an open, draining, or infected skin wound, or an ulcer.
11. Are currently infected (including carriers) with Human Immunodeficiency Virus (HIV), hepatitis B virus (HBV) or hepatitis C virus (HCV).
12. Have a history of known demyelinating diseases such as multiple sclerosis or optic neuritis.

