#### **12.1. Definitions**

##### **12.1.1. Adverse Event Definitions and Classifications**

###### **Adverse Event**

An AE is any untoward medical occurrence in a clinical study subject administered a medicinal (investigational or non-investigational) product. An AE does not necessarily have a causal relationship with the treatment. An AE can therefore be any unfavourable and unintended sign (including an abnormal finding), symptom, or disease temporally associated with the use of a medicinal (investigational or non-investigational) product, whether or not related to that medicinal

(investigational or non-investigational) product. (Definition per International Conference on Harmonisation [ICH]).

This includes any occurrence that is new in onset or aggravated in severity or frequency from the baseline condition, or abnormal results of diagnostic procedures, including laboratory test abnormalities.

Note: The sponsor collects AEs starting with the signing of the ICF (refer to Section [12.3.1](#), All AEs, for time of last AE recording).

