#### **12.3.1. All Adverse Events**

All AEs and special reporting situations, whether serious or non-serious, will be reported from the time a signed and dated ICF is obtained until completion of the subject's last study-related procedure, which may include contact for follow-up of safety. Serious adverse events, including those spontaneously reported to the investigator within 30 days after the last dose of study drug, must be reported using the Serious Adverse Event Form. The sponsor will evaluate any safety

information that is spontaneously reported by an investigator beyond the time frame specified in the protocol.

All events that meet the definition of a SAE will be reported as SAEs, regardless of whether they are protocol-specific assessments.

All AEs, regardless of seriousness, severity, or presumed relationship to study drug, must be recorded using medical terminology in the source document and the eCRF. Whenever possible, diagnoses should be given when signs and symptoms are due to a common etiology (eg, cough, runny nose, sneezing, sore throat, and head congestion should be reported as "upper respiratory infection"). Investigators must record in the eCRF their opinion concerning the relationship of the AE to study therapy. All measures required for AE management must be recorded in the source document and reported according to sponsor instructions.

The sponsor assumes responsibility for appropriate reporting of AEs to the regulatory authorities. The sponsor will also report to the investigator (and the head of the investigational institute where required) all suspected unexpected serious adverse reactions (SUSARs). The investigator (or sponsor where required) must report SUSARs to the appropriate Independent Ethics Committee (IEC) /Institutional Review Board (IRB) that approved the protocol unless otherwise required and documented by the IEC/IRB.

For all studies with an outpatient phase, including open-label studies, the subject must be provided with a "wallet (study) card" and instructed to carry this card with them for the duration of the study indicating the following:

- Study number
- Statement, in the local language(s), that the subject is participating in a clinical study
- Investigator's name and 24-hour contact telephone number
- Local sponsor's name and 24-hour contact telephone number (for medical staff only)
- Site number
- Subject number
- Any other information that is required to do an emergency breaking of the blind

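### The SAP's treatment-emergent rule has no limb for an adverse event that starts before the first dose and worsens on golimumab, so such an event can drop out of the five TEAE-labelled tables

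*SAP*

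**What the plan says.** The rule is in SAP section 5.2: "Any AE occurring at or after the initial administration of study drug through the day of last dose plus 8 weeks is considered" treatment-emergent. Two subsidiary rules follow. An event on the day of first dose with a missing time is taken as emergent. An event with a partial or missing date is also taken as emergent, "unless it is known to be prior to the first administration of study drug based on partial onset date or resolution date". Neither rule refers to a change in grade, frequency or seriousness.

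The same section then says: "All reported treatment-emergent adverse events will be included in the analysis". Of its seven summary tables, five carry the TEAE label: discontinuation, severity, relationship, special interest, and system organ class by preferred term. The tables for AEs and for serious AEs do not, and neither do the listings.

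Protocol section 12.1.1 takes a wider view of what an adverse event is: "This includes any occurrence that is new in onset or aggravated in severity or frequency from the baseline condition". Collection starts when the consent form is signed (12.1.1 and 12.3.1), so events with onset before dosing will be in the database.

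**The concern.** Safety over 24 weeks is the primary objective, and protocol section 9.2 promises the frequency of serious infections. An event that was minor at screening and worsened after an anti-TNF was started is one that the safety tables should show.

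The design allows such events. Exclusion criterion 9 in protocol section 4.2 says: "Less serious infections (eg, acute upper respiratory tract infection, simple urinary tract infection) need not be considered exclusionary at the discretion of the investigator". A patient can therefore be dosed with a minor infection already on record. If that infection worsens and the site updates the existing record, the record keeps its pre-dose onset date. Read by its dates, it is then not treatment-emergent.

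The possible error has one direction: an aggravated event can be lost from the TEAE counts. This also sits oddly with the rest of section 5.2, which resolves doubtful times and dates toward counting the event.

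**Working it through.** The plan gives no figure to reproduce. The sample size is a regulatory requirement (50 + 50 = 100) and no hypothesis is tested. The check is a reading of the texts, followed by a note on scale.

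**Step 1: what the date rule does.** I read the date on which an event occurs as the start date of its record, because the subsidiary rules work with the event day and time, the partial onset date and the resolution date. For an event that starts in screening and worsens after the first dose:

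| How the site records the worsening | Start date on the record | Status under SAP 5.2 | Five TEAE-labelled tables | Any-AE listing; SAE listing if serious |
|---|---|---|---|---|
| New record | After first dose | Emergent | Counted | Shown |
| Update to the existing record | Before first dose | Not emergent | Missing | Shown |

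**Step 2: whether the documents decide between the rows.** They do not. Section 12.1.1 makes aggravation an adverse event but gives no recording rule. Section 12.3.1 says "Whenever possible, diagnoses should be given when signs and symptoms are due to a common etiology", which concerns symptoms of one illness. It neither requires nor forbids a new record on worsening.

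**Step 3: effect of one affected patient.** If the patient has no other event in the same table row, the incidence moves by 1/50 = 2.0 points within an indication, or 1/100 = 1.0 point overall. If the patient already counts in that row, it does not move. Exact (Clopper-Pearson) 95% intervals:

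- n = 50: 0/50 = 0% (0 to 7.11%); 1/50 = 2.0% (0.05 to 10.65%)
- n = 100: 0/100 = 0% (0 to 3.62%); 1/100 = 1.0% (0.03 to 5.45%)

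**Step 4: how many, under assumptions only.** Protocol section 4 gives a screening window of 7 days. The rates below are assumed and appear in neither document: 0.5 to 2 adverse events per patient per 24 weeks (168 days), of which 10% to 25% of those starting before dosing later worsen.

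- Pre-dose events = 100 × rate × 7/168: 100 × 0.5 × 7/168 = 2.1, up to 100 × 2 × 7/168 = 8.3
- Worsening events: 2.1 × 0.10 = 0.2, up to 8.3 × 0.25 = 2.1

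These are events, so the number of patients is no larger. With an assumed probability p per patient, the chance of at least one affected patient is 1 − (1 − p)^n:

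| p | n = 50 | n = 100 |
|---|---|---|
| 0.5% | 22% | 39% |
| 1% | 40% | 63% |
| 2% | 64% | 87% |

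Only the events recorded as updates would be lost. That share is unknown, so these figures are upper limits under their own assumptions.

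**The case against.** The strongest reply is that the SAP says 'occurring' and does not redefine an adverse event. Under protocol section 12.1.1 a post-dose aggravation is itself an adverse event, and it occurs after the first dose, so it is already treatment-emergent. Recording conventions may sit in the CRF completion guidelines or the data capture manual, both listed in protocol section 15 and not available here. The nearest analogue, in section 12.3.2, has an event that prolongs a planned hospitalization reported as a new SAE. The exposed window is also short, and eligibility is checked again at Week 0.

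Much of this stands. A reader might infer that every event that worsens is lost from every TEAE table. The documents do not support that: a worsening entered as its own record meets the rule. Nor do they support saying that onset date alone decides, since the resolution date is also used when dates are partial.

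A reader might also infer that serious infections would vanish from the safety results. That does not follow either. The SAE listing is not restricted to TEAEs, and the SAE table carries no TEAE label. The sentence about including TEAEs in the analysis leaves the scope of that table unclear, but it does not show that the table is TEAE-only. Section 12.3.1 cannot be read as telling sites to merge successive diagnoses.

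What the reply does not remove is the dependence on recording practice. Nothing in either document requires a new record, and no SAP rule carries the protocol's aggravation wording into the derivation. The listings keep the event visible but give no incidence.

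**Conclusion.** The concern holds in conditional form. SAP section 5.2 classifies by event dates and is silent on worsening, so whether an aggravated pre-dose event appears in the five TEAE-labelled tables depends on how a site happened to record it. Two sites could record the same event differently, and it would be counted at one and not at the other.

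The conclusion rests on two conditions: that some events start between consent and first dose and then worsen, and that at least some of these are kept under the original onset date. Neither document excludes the second. The expected number is probably small and cannot be derived from the documents; the counts above rest on assumed rates. Each affected patient is worth up to 2.0 points in 50 or 1.0 point in 100, and any error in the TEAE tables understates harm. This is a cheap improvement to the primary safety analysis. It is not evidence that the safety results will be wrong.

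**What to change.** Four changes in SAP section 5.2:

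1. Define a TEAE as an adverse event whose onset is at or after the first dose, or whose onset is earlier but which increases in severity or frequency, or becomes serious, after the first dose. Keep the existing limit of 8 weeks after the last dose for both limbs.
2. Make the partial-date rule match: a known pre-dose onset excludes an event only if it did not worsen after the first dose.
3. Before the tables are run, review every adverse event record that was ongoing at the first dose. Use the date of worsening as the start of the emergent event where that date is recorded.
4. State whether the 'AEs' and 'SAEs' summary tables are limited to TEAEs.

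The cost is a few sentences, one derivation change and a check of what should be a small number of records. Adverse event percentages may rise slightly. The documents do not show whether the eCRF captures grade changes within a record. If it does not, the second limb cannot be fully programmed and will rely on manual review, which the SAP should say.
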